8.5 Subject Withdrawal Criteria

Subjects meeting the following criteria will be withdrawn from the trial:

1. Unable to tolerate study medication.
2. Failure to keep an accurate medication log.
3. Failure to keep study appointments.
4. Missing more than 10% of prescribed doses of study medication.*

**If a subject is missing more than 10% of prescribed doses, a discussion about the subject's continuation in the trial will take place between the Principal Investigator and the Sponsor-Investigator.*

Corticosteroids are the standard of care for the treatment of Duchenne muscular dystrophy and have a well-known side effect profile (see section 9.3). Subjects with any Grade 1 or higher (according to the Common Terminology Criteria for Adverse Events (CTCAE) version 4.03 and listed in section 11.1) adverse events that are anticipated and related to prednisolone use, will continue in the trial. Subjects with any Grade 2 or higher adverse events that are anticipated and are possibly, probably or definitely related to spironolactone use will have the study drug held and will be re-challenged in 1 week. If a subject experiences a recurrence of the adverse event, he may be withdrawn after discussion with the Clinical Safety Monitor. Subjects with any Grade 2 or higher adverse events that are unanticipated, may be withdrawn after discussion with the Clinical Safety Monitor. The Principal Investigator will determine a clinically appropriate tapering regimen with respect to assigned study drug and length of time on drug.

Principal Investigators must report all participant withdrawals to the Sponsor-Investigator within 48 hours of learning of the withdrawal. The Sponsor-Investigator will then notify the Clinical Safety Monitor of the withdrawal within 3 business days of the Sponsor-Investigator learning of the withdrawal.

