9. STUDY AGENT

Site pharmacies will dispense spironolactone and prednisolone per the site's standard procedures. In the rare instance of a subject not being able to tolerate prednisolone, an equivalent dose of prednisone may be provided as crushed tablets after approval by the Sponsor-Investigator.

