9.1 Dispensing of Study Agent

Subjects will be provided a supply of study drug at Day 0 and Month 3 (Day 90). A +/- 3 day window is acceptable for all visits after Day 0.

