10.2 Study Visits

10.2.1 Timeline

Table 3 Schedule of Assessments

Assessment	Visit 1	Study Drug Start ¹	Visit 2	Visit 3	Visit 4	Visit 5	Visit 6	Visit 7	Visit 8
	Screening		Week 1	Month 1	Month 2	Month 3	Month 4	Month 5	Month 6
	Day -14 to 0		Day 0	Day 7	Day 30	Day 60	Day 90	Day 120	Day 180
Research Purposes Only									
Echocardiogram (Echo) ²	X								X
Biomarkers Blood Draw (plasma and white blood cells)	X								X
Strength Testing/Dynamometry	X					X			X
Standard of Care									
Informed Consent	X								
AE Assessment		X	X	X	X	X	X	X	X
Concomitant Medications	X	X	X	X	X	X	X	X	X
Physical Exam	X					X			X
Skin Exam	X					X			X
Cushingoid Exam	X					X			X
Medical History Review	X					X			X
100 Meter Timed Test	X					X			X
Parent Survey			X	X	X		X	X	
4-Stair Climb	X					X			X
North Star Ambulatory Assessment (NSAA)	X					X			X
Time to Arise from Floor	X					X			X
Creatine Kinase	X								X
Gamma Glutamyl Transferase (GGT)	X					X			X
Creatinine	X					X			X
Blood Urea Nitrogen (BUN)	X					X			X
Glucose	X					X			X
Cystatin C	X					X			X
Electrolytes ³	X		X	X	X	X	X	X	X
Medication Dispensing ⁴		X ¹				X			
Vitals	X					X			X

1. Study drug will be dispensed and treatment initiated once eligibility is confirmed following receipt and review of results from screening visit procedures. The day study drug is started is considered Day 0.

2. A clinical echocardiogram within the previous 30 days prior to screening is acceptable for screening purposes.
3. Includes: Sodium, Potassium, Chloride, CO₂
4. Medication dispensing will occur every 90 days, beginning at the time of randomization.

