10.7.1 Long Term Monitoring

All adverse events occurring throughout the subject's participation in the trial through 30 days after the subject's final study visit will be documented and followed until resolution or stabilization. Research staff will contact subjects 30 days after the subject's final study visit to check for any new AEs and to obtain any new information regarding ongoing AEs.

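### Section 8.5 takes a boy who cannot tolerate study drug out of the trial and nothing provides a later 100M, so he probably has no Month 6 value for the primary test; keeping the visit is a cheap improvement

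*Combined protocol and SAP*

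**What the plan says.** The lead-in to the list in Section 8.5 is "Subjects meeting the following criteria will be withdrawn from the trial", and the list starts with "1. Unable to tolerate study medication". Item 4, on missed doses, has a footnote under which "a discussion about the subject's continuation in the trial will take place between the Principal Investigator and the Sponsor-Investigator". Item 1 has no such footnote.

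Other rules bear on how often item 1 is reached. Under 8.5, anticipated prednisolone-related events do not end participation. Anticipated spironolactone-related events of Grade 2 or higher lead to a hold and a re-challenge after one week. Only on recurrence may the boy be withdrawn, after discussion with the Clinical Safety Monitor. Unanticipated events of Grade 2 or higher may also lead to withdrawal after that discussion. Section 9 adds: "In the rare instance of a subject not being able to tolerate prednisolone, an equivalent dose of prednisone may be provided as crushed tablets".

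Table 3 (Section 10.2.1) schedules the "100 Meter Timed Test" at screening, Month 3 and Month 6, under its standard-of-care block. It has no early-termination visit. After withdrawal, 8.5 provides a taper and notices to the sponsor-investigator and the safety monitor. Section 10.7.1 provides a contact 30 days after the "final study visit to check for any new AEs and to obtain any new information regarding ongoing AEs". Section 11.3.2 provides examination until symptoms settle when drug is stopped for a related serious event. None of these names a 100M.

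Section 13 tests the change in age-corrected 100M from baseline to 6 months by TOST. It names no analysis set and no method for missing values.

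**The concern.** The primary test needs a Month 6 100M. Followed as written, item 1 removes the boy before that value is taken, and a value that was not collected cannot be recovered at analysis.

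The 10% drop-out allowance in Section 7.2 covers the number lost, not the selection. If boys who stop would have done worse than the rest of their arm, losing them from the spironolactone arm flatters spironolactone, and losing them from the prednisolone arm flatters prednisolone. If they would have done better, the signs reverse. The routes out also differ by arm: prednisolone has a substitute drug and a rule that keeps anticipated events in the trial, while spironolactone has a re-challenge but no substitute.

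Simply keeping everyone does not settle the matter. Section 8.5 itself says "Corticosteroids are the standard of care for the treatment of Duchenne muscular dystrophy", so a boy who stops spironolactone may well start a steroid, and that can pull the arms together. In an equivalence trial this also favours the conclusion being tested.

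**Working it through.** **1. The plan's own figure.** Inputs from Section 13: SD 7.8, margin ±10.6, 10 per group, power 80%. Alpha and the true difference are not stated; I assume 0.05 per side and 0. TOST declares equivalence when |D| + t(0.95, n1+n2−2) × s × √(1/n1+1/n2) < 10.6. Integrating exactly over the distribution of s gives 79.8% at 10 versus 10, so the stated power reproduces.

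**2. Is power at risk?** The enrolment allows for loss: 10/(1−0.10) = 11.1, rounded up to 12 per arm, 24 in all. Power at true difference 0:

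| n per arm | Power |
|---|---|
| 12 v 12 | 88.6% |
| 12 v 11 | 86.7% |
| 12 v 10 | 84.4% |
| 12 v 9 | 81.5% |

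A few one-sided losses leave power above 80%.

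**3. Selection, by illustration.** The documents give no stopping rate and no outcome for stoppers, so every input in this step and the next is assumed: k = 1 or 2 of 12 boys stop, and spironolactone is truly worse by exactly 10.6, where the chance of declaring equivalence should be 5%.

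(a) *Stoppers left out.* They do d worse than the rest of their arm, with d = 0.5 or 1 SD (3.9 or 7.8). Omitting them shifts the arm mean by k × d / 12.

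| k, d | Shift | Share of margin | Lost from spironolactone | Lost from prednisolone |
|---|---|---|---|---|
| 1, 3.9 | 0.325 | 3.1% | 6.1% | 4.1% |
| 1, 7.8 | 0.65 | 6.1% | 7.3% | 3.3% |
| 2, 3.9 | 0.65 | 6.1% | 7.3% | 3.3% |
| 2, 7.8 | 1.30 | 12.3% | 10.2% | 2.2% |

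(b) *Spironolactone stoppers kept in their arm, but on a steroid.* They regain a fraction f of the 10.6, so the shift is k × 10.6 × f / 12, at 12 versus 12.

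| k, f | Shift | Chance of equivalence |
|---|---|---|
| 1, 0.5 | 0.44 | 6.5% |
| 1, 1 | 0.88 | 8.4% |
| 2, 0.5 | 0.88 | 8.4% |
| 2, 1 | 1.77 | 13.4% |

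Neither set is safe alone.

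**4. Which rule for two sets?** I simulated both effects together: k = 1 or 2 spironolactone stoppers, d = 3.9 or 7.8, regaining none, half or all of 10.6.

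| Rule | Equivalence declared at the margin | Power at difference 0 |
|---|---|---|
| All randomised only | 4.5% to 13.3% | 87.0% to 88.3% |
| Still on drug only | 6.0% to 10.4% | 81.6% to 86.5% |
| Both required | about 4% to 9% | about 78% to 85% |
| Either accepted | about 7% to 14% | not needed here |

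Two sets with no rule for combining them leave the last row open. Requiring both is at least as strict as either set alone by construction.

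**The case against.** The best case against has four parts.

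- *Withdrawal is less automatic than item 1 sounds.* This stands, and it limits the point. The adverse event rules and the prednisone switch read naturally as steps before item 1, and the likeliest spironolactone route ends in a discretionary decision. Losses of 1 or 2 prednisolone boys in particular fit the text poorly. But once a boy is withdrawn, by whichever route, no section brings him back for a 100M.
- *The 100M is listed as standard of care, so a clinic value may exist.* It may. Nothing commits sites to collect it from a withdrawn boy, or to time it to the visit rule ("A +/- 3 day window is acceptable for all visits after Day 0"). That is why the claim is only that the value is probably missing.
- *The illustrations are all assumed.* True. They show a plausible scale and are not estimates.
- *An on-drug comparison is a defensible aim, and requiring both sets gains little.* Partly true. The synopsis objective speaks of six months of treatment, and when stoppers regain the full difference, requiring both lowers the error by only 0.3 to 1.1 points against the on-drug set alone. The worst-case power of about 78% is also slightly under the planned 80%. The gain is larger where stoppers do not regain it, and retained values let the reader see any disagreement.

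A reader might infer that the result will be biased towards spironolactone because exits are easier from that arm. The documents do not support this: they give no stopping rate for either drug and nothing on how stoppers fare.

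**Conclusion.** The point holds as a cheap improvement, not as an error in the plan. A boy withdrawn under item 1 before Month 6 probably contributes no change score to the primary TOST, and his absence is unlikely to be random. Probably few boys are affected, since Section 9 calls prednisolone intolerance rare and spironolactone events are re-challenged first. The actual number and the direction of bias cannot be computed from the documents.

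Two stronger readings should be resisted. One is that the trial loses its power: it does not, on the plan's SD and margin with 1 to 3 losses from one arm. The other is that analysing all randomised boys would be conservative: in an equivalence test with steroid rescue it need not be, as case (b) shows.

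The consequence is bounded by the aim in Section 5.2, pilot data for a longer study. The figures rest on alpha 0.05 per side, equal variances and the assumed stopper inputs.

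**What to change.** 1. **Section 8.5.** Move item 1 out of the withdrawal list, because rewording it under the present lead-in would contradict that lead-in. State separately: *A subject who cannot tolerate study medication, after the adverse event steps in this section and the Section 9 switch, stops study drug; this alone does not end trial participation.* In the two adverse event sentences, replace *may be withdrawn* with *may have study drug stopped*. State that items 2 and 4 (log and missed doses) do not apply after a recorded drug stop.
2. **Section 8.5 and a note to Table 3.** Add: *Unless consent is withdrawn, a subject who stops study drug keeps the remaining scheduled Month 3 and Month 6 100M tests; stop date, reason and any steroid started are recorded.*
3. **Section 13.** Report the TOST for all randomised boys with a Month 6 value, by randomised arm, and for boys still on assigned drug at Month 6, counting prednisone under Section 9 as assigned drug. State equivalence only if both sets show it; otherwise report the disagreement. Give the reason: omitting stoppers and steroid rescue can each pull the arms together.

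Cost: wording, a few eCRF fields and one extra TOST, with no extra patients and no new procedures. The downsides are up to two retained visits per stopper, which some families may decline, and power of about 78% to 85% at true difference 0 in the assumed cases, against 81.6% to 86.5% for the on-drug set alone.

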11. ASSESSMENT OF SAFETY

One of the primary objectives for this pilot clinical trial is safety. Withdrawal criteria are based on the development of unacceptable toxicity, as described in section 8.5.

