11.1 Adverse and Serious Adverse Events

11.1.1 Definition of Adverse Events

All Adverse Events (AE) will be reported to the Reviewing IRB at annual continuing reviews.

AEs will be collected throughout the trial from informed consent to 30 days after the subject's final study visit. All AEs that occur after any subject has been enrolled, before treatment, during treatment, or within 30 days after the last study visit, whether or not they are related to the study, must be recorded in the eCRF.

Adverse Event: Adverse event means any untoward medical occurrence associated with the use of a drug in humans, whether or not considered drug related.

Adverse events will be graded by the investigator and as used in the CTCAE v.4.03 accordingly:

1. Mild
2. Moderate
3. Severe
4. Life threatening or debilitating
5. Fatal.

Adverse Reaction: An adverse reaction means any adverse event caused by a drug. Adverse reactions are a subset of all suspected adverse reactions for which there is reason to conclude that the drug caused the event.

Suspected Adverse Reaction (21 CFR 312.32(a)): A suspected adverse reaction means any adverse event for which there is a reasonable possibility that the drug caused the adverse event. ‘Reasonable possibility’ means there is evidence to suggest a causal relationship between the drug and the adverse event. A suspected adverse reaction implies a lesser degree of certainty about causality than adverse reaction, which means any adverse event caused by a drug. Suspected adverse events will be reported to the Reviewing IRB at study closeout.

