11.1.3 Serious Adverse Event (SAE)

An adverse event or suspected adverse reaction is considered “serious” if, in the view of either the Sponsor-Investigator or Principal Investigator, it results in any of the following outcomes: death, a life-threatening adverse event, inpatient hospitalization or prolongation of existing hospitalization, a persistent or significant incapacity or substantial disruption of the ability to conduct normal life functions, or a congenital anomaly/birth defect. Important medical events that may not result in death, be life-threatening, or require hospitalization may be considered serious when, based upon appropriate medical judgment, they may jeopardize the subject and may require medical or surgical intervention to prevent one of the outcomes listed in this definition. Examples of such medical events include allergic bronchospasm requiring intensive treatment in an emergency room or at home, blood dyscrasias or convulsions that do not result in inpatient hospitalization, or the development of drug dependency or drug abuse. **A serious adverse events refers to a grade of 3, 4, or 5.**

All SAEs that occur after any subject has signed informed consent, before treatment, during treatment or within 30 days following the last study visit, whether or not they are related to the trial must be recorded.

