11.3.2 Safety Reporting

All serious adverse events that are **unexpected** and **possibly, probably, or definitely related** to the use of either study drug should be reported to the Sponsor-Investigator within **48 hours** of the Principal Investigator's initial receipt of the information. All other serious adverse events

should be reported to the Sponsor-Investigator within **7 days** of the Principal Investigator's initial receipt of the information.

The Sponsor-Investigator will report serious adverse events that are unexpected and possibly, probably, or definitely related to the use of either study drug to the Reviewing IRB according to regulatory requirements described as follows:

Any serious adverse event that is fatal or life-threatening, that is unexpected and related to the use of either study drug will be reported to the Reviewing IRB as soon as possible, but not later than **3 business days** after the Sponsor-Investigator's initial receipt of the information.

Serious adverse events that are unexpected and related to the use of either study drug, but are not fatal or life-threatening, will be reported to the Reviewing IRB as soon as possible, but not later than **3 business days** after the Sponsor-Investigator's initial receipt of the information.

If, after further evaluation, an unexpected serious adverse event initially considered not to be related to the use of either study drug is subsequently determined to be related, then the event will be reported to the Sponsor-Investigator within **48 hours** of the determination. The Sponsor-Investigator will report to the Reviewing IRB within **3 business days** of the Sponsor-Investigator learning of the determination.

Relevant additional clinical and laboratory data will become available following the initial serious adverse event report. Principal Investigators must report follow-up information to the Sponsor-Investigator within **48 hours** of initial receipt of the information. All follow-up information relevant to a serious adverse event that is unexpected and related to the use of either study drug will be reported to the Reviewing IRB within **3 business days** of the Sponsor-Investigator's initial receipt of the information.

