If a serious adverse event occurs within 30 days after a subject's final study visit and is determined to be unexpected and related to the use of either study drug, that event will be reported to the Reviewing IRB within **3 business days** of the Sponsor-Investigator learning of the determination.

Should a serious adverse event deemed possibly, probably or definitely related to the study agent occur during administration, the study agent will be discontinued, appropriate treatment will be given under medical supervision and the subject will be examined as frequently as necessary thereafter until symptoms cease or stabilize.

All new information and significant noncompliance indicating a new or increased risk or new safety issue as defined in the Reviewing IRB policies will be reported to the Sponsor-

Investigator within **48 hours** of the Principal Investigator learning of the information. The Sponsor-Investigator will report to the Reviewing IRB within **3 business days** of the Sponsor-Investigator's initial receipt of the information. This includes deviations from the protocol that harmed subjects or others or that indicates subjects or others might be at an increased risk of harm.

The Sponsor-Investigator will inform the Clinical Safety Monitor of all serious adverse events regardless of severity, relatedness, or expectedness and of all instances of significant non-compliance impacting patient safety within **48 hours** of the Sponsor-Investigator's initial receipt of the information.

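### Section 8.5 directs spironolactone re-challenge at one week after any anticipated, related event of Grade 2 or higher, with no upper grade and no recovery condition

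*Combined protocol and SAP*

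**What the plan says.** Section 8.5 defines the group as "Subjects with any Grade 2 or higher adverse events that are anticipated and are possibly, probably or definitely related to spironolactone use", and the instruction is that such boys, with events "related to spironolactone use will have the study drug held and will be re-challenged in 1 week". If the event recurs, the boy may be withdrawn after discussion with the Clinical Safety Monitor. Section 11 refers back to this text: "Withdrawal criteria are based on the development of unacceptable toxicity, as described in section 8.5".

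Four other places bear on the same events:

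- Section 11.1.1 labels Grade 4 "Life threatening or debilitating".
- Section 11.1.3 states: "A serious adverse events refers to a grade of 3, 4, or 5".
- Section 11.3.2 states: "Should a serious adverse event deemed possibly, probably or definitely related to the study agent occur during administration, the study agent will be discontinued". It continues: "appropriate treatment will be given under medical supervision and the subject will be examined as frequently as necessary thereafter until symptoms cease or stabilize". It mentions no restart.
- Section 11.4 includes raised potassium among the anticipated effects of spironolactone, without naming a grade.

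**The concern.** Hold and re-challenge is a reasonable rule for a moderate event that has settled. Here it is written as a mandatory step for everything from Grade 2 upward. It depends on neither a repeat laboratory value, nor a fall in grade, nor anyone outside the site agreeing. The event that matters most is hyperkalemia. A site that follows 8.5 to the letter could restart spironolactone at one week in a boy whose Grade 3 or 4 potassium has not been shown to have come down.

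The trial runs at four to seven centers with no central laboratory, so sites may also handle the same result differently. Some investigators may turn to the discontinuation sentence in 11.3.2 instead of 8.5. What is at stake is the safety of individual boys. The primary analysis is not affected.

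**Working it through.** The protocol gives no figure to reproduce. The check sets its provisions side by side, with some date arithmetic.

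1. **Does 8.5 reach Grades 3 and 4?** The trigger is Grade 2 or higher on a five-grade scale. Grade 5 is fatal, so re-challenge can apply to Grades 2, 3 and 4. Raised potassium is anticipated under 11.4 at any grade. A related Grade 3 or 4 hyperkalemia is therefore inside the rule as written.

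2. **Is recovery required before the restart?** Section 8.5 does not require it. Section 10.1 says only that clinically significant on-study results may be repeated. Section 8.4 is firmer on repeat testing, but it stands under the baseline heading. Section 11.3.5 requires follow-up to resolution or stabilization. None of these is tied to restarting the drug.

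3. **Would a scheduled test fill the gap?** Section 10.2.1 (Table 3) places electrolytes at Day 7, Day 30 and Day 60, among other visits. Assume the hold starts on the day of the test:
   - Found at Day 7: restart at 7 + 7 = Day 14. The next scheduled potassium is Day 30, which is 30 − 14 = 16 days after the restart.
   - Found at Day 30: restart at 30 + 7 = Day 37. The next is Day 60, which is 60 − 37 = 23 days after the restart.

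   In both cases no scheduled potassium falls between the hold and the restart.

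4. **Would the Clinical Safety Monitor see the case first?** Section 8.5 calls for discussion only on recurrence, and laboratory review under 12.1 is monthly. Under 11.3.2, serious events other than those both unexpected and related "should be reported to the Sponsor-Investigator within 7 days of the" site investigator learning of them. The Sponsor-Investigator then has 48 hours to inform the Monitor.
   - Expected serious event: 7 days + 2 days = 9 days, later than the 7-day restart.
   - Unexpected and related serious event: 2 days + 2 days = 4 days, before the restart.

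   These are maximum limits, not expected delays.

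5. **Does 8.5 conflict with 11.3.2?** Section 11.1.3 makes Grades 3 to 5 serious, so a related Grade 3 or 4 event could fall under both rules. Whether it does depends on terms the protocol leaves open.

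| Reading | Result for an anticipated, related Grade 3 or 4 event |
|---|---|
| *During administration* means the dosing period, and discontinuation is permanent | 11.3.2 stops the drug and 8.5 restarts it: direct conflict |
| The dosing period, but discontinuation is temporary | No conflict; 8.5 governs the restart, still without a recovery condition |
| *During administration* means the moment of dosing | 11.3.2 rarely applies; 8.5 alone governs, still without a recovery condition |
| Greater severity makes the event unexpected (11.1.2), and unexpected equals unanticipated | 8.5's other rule applies: possible withdrawal after discussion with the Monitor, and no automatic re-challenge |

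Only the last reading removes automatic re-challenge, and no provision equates the two terms. The halting rule in 11.4 does not decide the matter, because it covers unanticipated events and halts enrollment, not a boy's dosing.

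**The case against.** A reader might infer that the protocol flatly contradicts itself. The documents do not support that. The discontinuation sentence in 11.3.2 is limited to events during administration, a phrase left undefined, and a potassium value from a scheduled or offsite blood draw is not plainly such an event. The narrow reading also fits better with the other arm. The sentence refers to the study agent, and Section 9 uses that term for both drugs. Read as covering six months of dosing, it would also run against 8.5's rule that boys with anticipated prednisolone-related events continue in the trial. On the other side, daily oral dosing over six months makes the dosing period a natural meaning. The conflict is therefore possible, and no more than that.

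A reader might also infer that a site is forced to restart the drug in a boy in danger. That is not so. Sections 15.1 and 18.2 allow departures from the protocol to protect subjects, and 8.5 withdraws a boy who cannot tolerate the medication. Section 11.1.2 gives an arguable basis for treating a severe form of a known toxicity as unexpected. The exclusions in 8.2 and the prohibited medications in 10.8.1 lower the chance of hyperkalemia, and nothing prevents an early call to the Monitor.

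All of this stands and narrows the point. But these are general powers or debatable readings. Intolerance is not defined by grade, and a safe course should not depend on departing from a mandatory instruction.

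**Conclusion.** The missing upper grade and the missing recovery condition in 8.5 are established with high confidence from the text. They amount to a stated rule that is unsafe if followed literally, and they should be corrected. The conflict with 11.3.2 is held with moderate confidence only. It requires that *during administration* means the dosing period, that discontinuation is permanent, and that greater severity does not move the event out of the anticipated class.

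The grades affected are 3 and 4, plus Grade 2 events that have not resolved by one week. The frequency cannot be estimated, because the protocol gives no rate of hyperkalemia or of any other spironolactone event. The timing gap, 9 days against 7, shows that Monitor review before the restart is not assured. It does not show that review would usually come late.

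**What to change.** Change 8.5 only:

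- Limit automatic hold and re-challenge to non-serious Grade 2 spironolactone-related events that have resolved. For potassium, require a repeat value that the Study Doctor confirms is acceptable, for example within the site's normal range.
- For spironolactone-related events that are serious or Grade 3 or higher, stop spironolactone and do not re-challenge unless this is agreed beforehand with the Clinical Safety Monitor.

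Leave the words *during administration* in 11.3.2 as they are, or confine any change there to spironolactone. A general extension to the whole treatment period would require stopping prednisolone for any related Grade 3 or higher event, against 8.5's provisions on continuing in the trial and on tapering.

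The cost is a clarifying amendment, one repeat potassium before a potassium-related re-challenge, an earlier call to the Monitor when re-challenge is wanted after a serious or Grade 3 or higher event, and possibly a few more spironolactone discontinuations. No endpoint or sample size changes.
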